## 8.2 CLASSIFICATION OF AN ADVERSE EVENT

### 8.2.1 SEVERITY OF EVENT

For all AEs the following guidelines will be used to describe severity.

- **Mild** – Events require minimal or no treatment and do not interfere with the participant's daily activities.
- **Moderate** – Events result in a low level of inconvenience or concern with the therapeutic measures. Moderate events may cause some interference with functioning.
- **Severe** – Events interrupt a participant's usual daily activity and may require systemic drug therapy or other treatment. Severe events are usually potentially life-threatening or incapacitating.

### 8.2.2 RELATIONSHIP TO STUDY AGENT

The clinician's assessment of an AE's relationship to the study device is part of the documentation process, but it is not a factor in determining what is or is not reported in the study. If there is any doubt as to whether a clinical observation is an AE, the event should be reported. All AEs must have their relationship to study agent assessed. In a clinical trial, the study product must always be suspect. To help assess, the following guidelines are used.

- **Related** – The AE is known to occur with the study agent, there is a reasonable possibility that the study agent caused the AE, or there is a temporal relationship between the study agent and event. Reasonable possibility means that there is evidence to suggest a causal relationship between the study agent and the AE.
- **Not Related** – There is not a reasonable possibility that the administration of the study agent caused the event, there is no temporal relationship between the study agent and event onset, or an alternate etiology has been established.

## 8.3 TIME PERIOD AND FREQUENCY FOR EVENT ASSESSMENT AND FOLLOW-UP

The occurrence of an AE or SAE may come to the attention of study personnel during study visits and interviews of a study participant presenting for medical care, or upon review by a study monitor. All AEs including local and systemic reactions not meeting the criteria for SAEs will be captured on the appropriate CRF. Information to be collected includes event description, time of onset, clinician's assessment of severity, relationship to study product (assessed only by those with the training and authority to make a diagnosis), and time of resolution/stabilization of the event. All AEs occurring while on study must be documented appropriately regardless of relationship. All AEs will be followed to adequate resolution.

Any medical condition that is present at the time that the participant is screened will be considered as baseline and not reported as an AE. However, if the study participant's condition deteriorates at any time during the study, it will be recorded as an AE. All AEs will be recorded in the data collection system throughout the study.

The PI will record all reportable events with start dates occurring any time after informed consent is obtained until the last day of study participation. At each study visit, the investigator will inquire about the occurrence of AE/SAEs since the last visit. Events will be followed for outcome information until resolution or stabilization.

#### 8.4 ADVERSE EVENT REPORTING PROCEDURES

All AEs will be monitored from study enrollment through completion of this study. All AEs will be recorded in the database. The Investigator is required to complete the adverse event CRF at each study visit, if an adverse event occurs. A description of the event, including the start date, resolution date, action taken and the outcome should be provided, along with the investigator's assessment of the relationship between the AE and the study treatment.

All AEs should be followed until the event is resolved or judged to be chronically stable. The Site will provide relevant follow-up information to the sponsor and/or their designated representative.

All SAEs must be reported to the sponsor and/or their designated representative, the respective IRB within 24 hours of the site becoming aware of the event. A completed SAE CRF must be submitted to the sponsor or designee within five (5) working days of the event. The minimum required data to be recorded for an SAE includes: date of event, type of event, duration of event, severity, action taken, outcome and, if appropriate, causality and possible relationship to the investigational device. The Investigator should report all serious adverse events to the reviewing IRB, as required.

To ensure participant safety, each UADE must be reported to the sponsor and the IRB/EC immediately, but not later than 10 working days of learning of its occurrence. The SAE CRF and any supporting documentation should then be immediately sent to the sponsor who will be responsible for notifying the FDA.

If there is a device malfunction or other observation, the Device Observation CRF requires the Investigator to notify the Sponsor immediately and indicate if the observation resulted in an adverse event and indicate if complications are related to the device, procedure or underlying disease.

In the event of a suspected observation or device problem, the device shall be returned to the Sponsor for analysis. Instructions for returning the investigational device are included in the Study Reference Manual.

#### 8.5 SAFETY OVERSIGHT

Safety oversight will be under the direction of a Medical Monitor with the appropriate expertise. The Medical Monitor will review AEs, SAEs and UADEs according to the AE/SAE Handling Plan. The Medical Monitor will provide its input to the study sponsor. Given the low risk nature of the product, there will be no formal data safety monitoring board (DSMB).

### 9 CLINICAL MONITORING

Clinical site monitoring is conducted to ensure that the rights and well-being of human subjects are protected, that the reported trial data are accurate, complete, and verifiable, and that the conduct of the trial is in compliance with the currently approved protocol/amendment(s), with GCP, and with applicable regulatory requirement(s).

- [REDACTED] or her designee will be the monitor for the sites in this study.
- On-site monitoring visits for data verification will occur only once at the end of the study.
- This monitoring visit will include 100% data verification.
- Monitoring reports will be distributed to the PI and study sponsor.
- Independent audits will not be conducted.
- Each clinical site will perform internal quality management of study conduct, data collection, documentation and completion.

The sponsor or their designee will monitor either on site or remotely, as applicable. Monitoring and auditing procedures developed by the sponsor or their designee will be followed. The investigator must make available all subject records and regulatory documentation at every monitoring visit. The monitor will evaluate the CRFs for completeness and clarity, and for verification of the data with any source documents. Any discrepancies found are to be clarified by the investigator or designee. Consideration for medical confidentiality and data protection will be maintained as best as possible at every visit.

## 10 STATISTICAL CONSIDERATIONS

The overall objective of this study is to demonstrate the safety and effectiveness of DCTclock as an adjunctive tool for use by clinicians to evaluate cognitive function in adults aged 55-95. From an effectiveness perspective, the study intends to prove that:

- a. DCTclock is non-inferior to the reference standard, MMSE, in identifying unimpaired and impaired test subjects.
- b. DCTclock shows test-retest reliability comparable to that of the MMSE.

The specific endpoints are as follows:

Primary endpoint: DCTclock and MMSE assessment of impaired, unimpaired or indeterminate/intermediate status. The primary analysis will assess agreement of DCTclock with the reference standard, MMSE, in identifying unimpaired and impaired test subjects.

Secondary endpoint: DCTclock scores, MMSE scores and assessment of DCTclock and MMSE impaired and unimpaired status at each of two time points. The secondary analysis will assess the DCTclock test-retest reliability and descriptively compare it to that of MMSE.

Additional endpoint: DCTclock scores, MMSE scores and neuropsychology battery scores. The goal of analysis on these endpoints is to assess construct validity of DCTclock. Specifically, the goal is to compare scores from the repeated administration of DCTclock to the repeated administration of a battery of neuropsychological tests, to characterize the psychometric properties of DCTclock and to compare those properties to the properties of MMSE.

Safety endpoint: incidence of device related adverse events.

### 10.1 STATISTICAL AND ANALYTICAL PLANS

There will be a formal statistical analysis plan (SAP) for this study outlining in detail the analyses to be provided for all variables collected during the study. The sections below summarize the analysis for the primary and secondary safety and effectiveness endpoints.

### 10.2 STATISTICAL HYPOTHESES

Participants will be categorized as impaired, not impaired or indeterminate/intermediate for each of DCTclock, MMSE, and MoCA using the first measurement obtained on each participant. A 3-by-3 table, with the rows being the DCTclock/MMSE cognitive status and with columns being the MoCA cognitive status, will be generated as follows.

		MoCA			
		Impaired	Indeterminate/Intermediate	Unimpaired	Total
DCTclock/ MMSE	Impaired	a	b	c	a+b+c
	Indeterminate/ Intermediate	d	e	f	d+e+f
	Unimpaired	g	h	i	g+h+i
	Total	a+d+g	b+e+h	c+f+i	a+b+c+d+e+f+g+h+i

### 10.3 ANALYSIS DATASETS

- Intention-to-Treat (ITT) Analysis Dataset: all enrolled participants
- Evaluable Analysis Dataset: all enrolled participants undergoing cognitive testing with both DCTclock and MMSE and who are not performing suboptimally (as determined by the Reliable Digit Score). This is the primary analysis set for effectiveness.
- Safety Analysis Dataset: all enrolled participants undergoing cognitive testing with DCTclock. This is the primary analysis set for safety.

### 10.4 DESCRIPTION OF STATISTICAL METHODS

#### 10.4.1 GENERAL APPROACH

All subjects will undergo testing with DCTclock, MMSE, and MoCA. A non-inferiority analysis using a two-sided tests (TOST) approach will be conducted comparing the quadratic weighted kappa between DCTclock and MoCA to the quadratic weighted kappa between MMSE and MoCA.

The remaining analysis comparing DCTclock to MMSE will be descriptive, providing two-sided 95% confidence intervals of important parameters when necessary.

Descriptive statistics include sample size, mean, standard deviation, median and quartiles for continuous variables, and counts and percents for categorical variables. All confidence intervals will be two-sided 95% confidence intervals, and all p-values will be two-sided, using a two-sided 0.05 level of significance. There will be no imputation of missing data. Statistical analysis will be conducted with R version 3.4 or higher.

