#### 10.4.2 ANALYSIS OF THE PRIMARY EFFECTIVENESS ENDPOINT

The primary effectiveness analysis will be carried out using quadratic weighted kappa scores. A two-sided test (TOST) approach will be conducted, comparing the agreement between the MMSE and DCTclock scores with MoCA scores.

The kappa statistics will be calculated from the following table:

MoCA	
------	--

DCTclock/ MMSE		Impaired	Indeterminate/intermediate	Unimpaired	Total
	Impaired	a	b	c	a+b+c
	Indeterminate /intermediate	d	e	f	d+e+f
	Unimpaired	g	h	i	g+h+i
	Total	a+d+g	b+e+h	c+f+i	a+b+c+d+e+f+ g+h+i

This portion of the analysis will be carried out on the primary endpoint population and will only include scores from the first examination.

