### 10.4.3 SAMPLE SIZE

Approximately 500 participants will be enrolled to obtain 400 evaluable participants. The evaluable sample size is the same as the evaluable sample size used in “De Novo Classification Request for Cognivue”. The primary null and alternative hypotheses are:

$$H_0: \kappa \leq 0.40 \quad \text{vs.} \quad H_1: \kappa > 0.40$$

where  $\kappa$  is the quadratic weighted kappa statistic calculated from the above DCT-MMSE classification table. Power for quadratic weighted kappa requires assumptions of the values on the diagonal and off-diagonal of the table, which is a large number of assumptions. Power will thus be calculated for the unweighted kappa which requires fewer assumptions. It is assumed that the quadratic weighted kappa will be similar to or larger in magnitude than the unweighted kappa and with similar standard error as the unweighted kappa, so the study will be powered to show that the unweighted kappa  $> 0.4$  with the expectation it will then be sufficiently powered to show that the quadratic weighted kappa  $> 0.4$ . An evaluable sample size of 400 subjects yields at least 80% power to reject the above null hypothesis at one-sided 0.025 level of significance under the assumptions that: (1) the true kappa is 0.52 or more; (2) the marginal percentage of participants categorized as impaired is between 20% and 42.5% for DCTclock; (3) the marginal percentage of participants categorized as impaired for MMSE is the same as that for DCTclock; (4) the marginal percentage of participants categorized as unimpaired for DCTclock is the same as the marginal percentage of participants categorized as impaired for DCTclock; (5) the marginal percentage of participants categorized as unimpaired for MMSE is the same as that for DCTclock; and (6) the marginal percentage of participants categorized as indeterminate is between 15% and 60% for each of DCTclock and MMSE and is equivalent between DCTclock and MMSE.

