#### 10.4.10 SUB-GROUP ANALYSIS

All above effectiveness analyses (with the exception of the formal hypothesis test of the weighted kappa) may be repeated by (1) age (below median age, at or above median age); (2) sex; (3) education level; (4) language fluency test score (below median, at or above median) (5) medical history; and (6) current medications.

In addition, it is expected that the DCTclock test’s ability to identify impaired participants exceeds that of MMSE when participants are mildly impaired. Thus, for participants who score unimpaired on MMSE but impaired on DCTclock, scores on the neuropsychology battery test may be further inspected as follows to assess how often the DCTclock yielded the correct diagnosis in these cases. Specifically, the following will be presented on this subset of participants (when available):

- Percentage of participants scoring in the impaired range on the MoCA test (25 or below)
- Percentage of participants scoring 1.5 standard deviations below the mean on two or more of the following tests (Benton Judgement of Line, Rey Complex Figure, DKEFs, Digit Span, Blocks, Trails, Symbol Digit).
- Percentage of participants 2 standard deviations below the mean on one of the following tests (Benton Judgement of Line, Rey Complex Figure, DKEFs, Digit Span, Blocks, Trails, Symbol Digit).

---

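### The primary kappa comparison is named as TOST, a two-bound equivalence procedure, although the stated aim is one-sided non-inferiority

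*Protocol*

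**What the plan says.** Protocol section 10 lists what the study is meant to prove on effectiveness. Item (a) is that "DCTclock is non-inferior to the reference standard, MMSE, in identifying unimpaired and impaired test subjects". That claim runs in one direction.

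Section 10.4.1 names the procedure: "A non-inferiority analysis using a two-sided tests (TOST) approach will be conducted comparing the quadratic weighted kappa between DCTclock and MoCA", with the MMSE-MoCA weighted kappa as comparator. Any other comparison of DCTclock with MMSE is to be descriptive. Section 10.4.2, which governs the primary effectiveness endpoint, no longer says non-inferiority: "A two-sided test (TOST) approach will be conducted, comparing the agreement between the MMSE and DCTclock scores with MoCA scores". Neither section gives a margin, an upper bound or a pass rule.

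On error levels, section 10.4.1 states "All confidence intervals will be two-sided 95% confidence intervals" and "all p-values will be two-sided, using a two-sided 0.05 level of significance". Section 10.4.3 works "at one-sided 0.025 level of significance", but for another hypothesis: that the weighted kappa of the DCTclock-MMSE table is above 0.40. Section 10.4.10 expects that the DCTclock test's "ability to identify impaired participants exceeds that of MMSE when participants are mildly impaired".

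**The concern.** Non-inferiority and TOST have different pass rules. Write D for kappa(DCTclock, MoCA) minus kappa(MMSE, MoCA), and M for the margin. Non-inferiority needs evidence that D > -M. TOST needs evidence that D > -M and also that D < +M. The second requirement has no place in objective (a) and counts a large advantage of DCTclock as a failure.

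The acronym is also expanded wrongly in both sections, as two-sided test(s) instead of two one-sided tests, so a reader cannot tell which rule is meant. Because the other comparisons with MMSE are descriptive, no further formal comparison of DCTclock with MMSE against MoCA could recover the claim if the upper test failed.

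**Working it through.** **1. The plan's own figure.** Section 10.4.3 claims at least 80% power with 400 evaluable participants for kappa > 0.40 when the true unweighted kappa is 0.52, at one-sided 0.025. The check uses the large-sample (Fleiss-Cohen-Everitt) standard error, equal margins for both tests and common-correlation cells:

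Power = Φ((0.12 - 1.96 × SE0) / SE1), where SE0 is taken at kappa 0.40 and SE1 at kappa 0.52.

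| Impaired / indeterminate / unimpaired | SE0 | SE1 | Power |
|---|---|---|---|
| 20 / 60 / 20 | 0.0406 | 0.0387 | 85.2% |
| equal thirds | 0.0367 | 0.0350 | 91.5% |
| 42.5 / 15 / 42.5 | 0.0388 | 0.0368 | 88.3% |

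The claim reproduces. It concerns one kappa from the DCTclock-MMSE table, so it says nothing about the power to compare two kappas with MoCA.

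**2. Error levels.** Two-sided 0.05 is 0.05 / 2 = 0.025 per side. A two-sided 95% interval also leaves 0.025 per side. Section 10.4.3 uses one-sided 0.025. The three agree.

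**3. Pass probabilities for D.** By normal approximation, with d the true difference, SE its standard error and z = 1.96:

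- Non-inferiority: L = Φ((d + M)/SE - z).
- TOST: L + U - 1 (or 0 if negative), where U = Φ((M - d)/SE - z).

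The protocol gives neither M nor SE. SE = 0.043 is an assumption from a simulation of 400 participants with latent-normal scores and a 30/40/30 split on all three tests. M = 0.10 is for illustration only.

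- d = 0: L = Φ(0.10/0.043 - 1.96) = Φ(0.366) = 0.643, and U is the same. TOST = 2 × 0.643 - 1 = 0.285 (0.2853 before rounding L). So **64% against 29%**.
- d = +0.09: L = Φ(0.19/0.043 - 1.96) = Φ(2.459) = 0.993. U = Φ(0.01/0.043 - 1.96) = Φ(-1.727) = 0.042. TOST = 0.993 + 0.042 - 1 = 0.035. So **99% against about 3.5%**. At 0.05 per side (z = 1.645), TOST gives 7.6%.

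**4. Sensitivity to the assumptions**, at 0.025 per side. SE 0.053 and 0.040 correspond to 0.045 per kappa with correlation 0.3 and 0.6: 0.045 × √(2 × 0.7) = 0.0532 and 0.045 × √(2 × 0.4) = 0.0402.

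| SE | M | d | Non-inferiority | TOST |
|---|---|---|---|---|
| 0.043 | 0.15 | 0 | 94% | 87% |
| 0.053 | 0.10 | 0 | 47% | 0% |
| 0.053 | 0.15 | 0 | 80% | 61% |
| 0.053 | 0.15 | +0.10 | 99.7% | 15% |
| 0.053 | 0.15 | +0.20 | about 100% | 0.2% |
| 0.040 | 0.20 | 0 | 99.9% | 99.7% |

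The loss at d = 0 ranges from total to negligible as the margin widens relative to SE. The zero in the second row arises because the half-width, 1.96 × 0.0532 = 0.104, exceeds the margin.

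**5. What does not depend on M or SE.** At d = M, U = Φ(-z), which is the per-side level. So once the true advantage reaches the margin, TOST passes with probability at most 2.5% at 0.025 per side, or 5% at 0.05 per side.

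**6. False passes.** At d = -M the two procedures pass at about the same rate: 0.025 at 0.025 per side and 0.05 at 0.05 per side. At a given level the upper test costs power and does not add false claims.

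**The case against.** The strongest reply is that section 10.4.1 itself calls the analysis non-inferiority, so the authors may have meant to run two one-sided tests and read the result from the lower one. The SAP, which is not shown, may say so. That is a plausible intention, and it is why the consequence is conditional on a literal reading. It does not remove the point. Nothing in the protocol limits the procedure to the lower test, section 10.4.2 drops the word non-inferiority, and calling the test two-sided points towards both bounds. The protocol names a procedure that does not match its aim, which is different from leaving detail to the SAP.

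It can also be said that the margins are assumed and that the most striking results sit at or near them, where TOST must fail by construction. This stands. The percentages illustrate a mechanism and do not forecast the trial. Section 10.4.10 expects an advantage only in mild impairment. It makes the favourable direction realistic but does not predict an overall kappa advantage of 0.09 or more.

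A reader might further infer that the error level conflicts with the stated 0.025, or that the false-claim risk is 5%. The documents do not support this. The stated levels are the same per side, no 90% interval or 0.05-per-side TOST is specified, and the 0.025 in section 10.4.3 belongs to the DCTclock-MMSE hypothesis. What remains is an ambiguity: TOST is conventionally run at 0.05 per side, and the protocol does not say whether its general 0.025 per side applies instead.

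**Conclusion.** The point holds as a contradiction between aim and named procedure: one-sided non-inferiority in section 10, TOST in sections 10.4.1 and 10.4.2. Under a literal TOST, a DCTclock whose true advantage reaches the margin passes with probability no greater than the per-side level, whatever the margin or standard error. The loss for smaller advantages, or for none, depends on both. It is large in the illustration (SE 0.043, margin 0.10) and negligible with a wide margin.

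It would be too strong to say that DCTclock will fail if it is better, because the protocol sets no upper bound and a lower-test-only reading is possible. It would also be too strong to treat this comparison as the settled primary test: section 10.4.3 labels a different hypothesis as primary, and the stated power belongs to that one. Since the wording governs a pass rule for the primary endpoint, it should be settled before the data are analysed.

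**What to change.** - In sections 10.4.1 and 10.4.2, replace TOST with a single one-sided non-inferiority test at 0.025. The lower limit of the two-sided 95% confidence interval for kappa(DCTclock, MoCA) minus kappa(MMSE, MoCA) must exceed minus a pre-stated margin. Drop the upper test. This also settles the level, in line with the general interval rule in 10.4.1.
- State that the interval accounts for the pairing, since all three tests are taken by the same participants and both kappas share MoCA. Resampling whole participants is one way.
- Reconcile this with section 10.4.3: say which hypothesis is primary, or how the two relate, and give power for the kappa difference if that comparison decides success.

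The cost is wording in these sections and matching SAP text, a justified margin, and a power calculation for the difference if it is primary. No new data are needed. If that calculation shows too little power at 400 evaluable participants, the sample size would have to be reconsidered.

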#### 10.4.2 ANALYSIS OF THE PRIMARY EFFECTIVENESS ENDPOINT

The primary effectiveness analysis will be carried out using quadratic weighted kappa scores. A two-sided test (TOST) approach will be conducted, comparing the agreement between the MMSE and DCTclock scores with MoCA scores.

The kappa statistics will be calculated from the following table:

MoCA	
------	--

DCTclock/ MMSE		Impaired	Indeterminate/intermediate	Unimpaired	Total
	Impaired	a	b	c	a+b+c
	Indeterminate /intermediate	d	e	f	d+e+f
	Unimpaired	g	h	i	g+h+i
	Total	a+d+g	b+e+h	c+f+i	a+b+c+d+e+f+ g+h+i

This portion of the analysis will be carried out on the primary endpoint population and will only include scores from the first examination.

